8.5 Re-Screening

In some cases it is possible that potential participants will need to be re-screened, for example:

- If a person consents to participate, meets the eligibility criteria but there is a delay in starting due to a change in situation (family issues, individual request for attending private matter, etc);
- If the person previously failed eligibility due to an acute event that has now resolved; or
- Medications have now stabilised

In these situations, if randomisation has not occurred;

- A new Eligibility Case Report Form is used
- A new ID number is assigned to the participant
- The participant is flagged as having been re-screened on both the Case Report Form and the site master list
- The Eligibility Case Report Form is completed as if being fully screened, data is not copied form one form to the next, but completed using the current clinical situation as documented within the patient clinical notes.

It is not appropriate to re-screen a person if they have previously failed to meet the eligibility criteria and there have been no further changes or treatments that would now indicate that the patient may be suitable.

More detail is provided within the Standard Operating Procedure for re-screening (6.5.2, Rescreening).

8.6 Procedure to request randomisation

Pharmacy will be contacted whenever a person is under-going the screening process to warn them of a potential trial candidate. This will be followed up by a confirmatory call as soon as the person's eligibility has been confirmed. The randomisation request will take the form of the prescription of the study drugs.

The site clinical trials pharmacist will identify the study drugs for the participant according to the allocation determined in the supplied schedule, and label the bottles providing the details as described above.

The allocation will be recorded on the schedule along with the date of allocation, the signature of the pharmacist preparing the syringe and the patient ID number.

Participant randomisation will be registered with the coordinating site. PaCCSC has a Standard Operating Procedure for Randomisation (4.7.1, Randomisation), this procedure is to be followed. In summary, the procedure outlines that on randomisation of a participant, the site pharmacy is to fax a notification to the coordinating site. This notice will be monitored alongside the participant eligibility as entered onto the on-line data base from Eligibility CRF.

Participants will not be randomised twice. Participation during a previous admission will exclude any future participation.

8.7 Prescription of study drugs

All prescriptions for the use of investigational products for clinical trials must be:

- Completed by a person authorised to do so
 - o the principle site investigator
 - o sub/co investigators
 - those medically authorised to prescribe the specific product under investigation
- Completed on a hospital prescription form and detail full description of the
 - o participant details
 - o study protocol number
 - o medicine (this will be melatonin/placebo)
 - o dose (this will specify the dose level/s)
 - frequency
 - o route

In this study the prescription will therefore read:

Melatonin prolonged release (2mg)/ placebo. Take one tablet (whole) every night at 2000 hours during admission. Supply 7 tablets.

The medication will be dispensed to the ward, with up to one week supply at a time dependent on the ward procedures. Smaller numbers of tablets can be dispensed if preferred.

8.8 Treatment commencement

All baseline assessments will be undertaken as soon as eligibility is confirmed, and treatment initiated as soon as practicable.

All baseline assessments will be undertaken immediately before the first study dose on day 1, treatment will be then initiated on the first night at 2100 hours (\pm one hour). Local hospital procedures are to be followed regarding checking of study medicine.

8.9 Daily assessments

Participants will be visited daily by the study nurse in the inpatient unit, at the same time in the morning of each day. Prior to reviewing the participant, the study nurse will check with the unit nursing staff regarding the participant's condition, and any recent events.

During the visit, the study nurse will take the measures and assessments as outlined in the table of study measures and record the visit in the Case Report Form for that time point. This visit will also be recorded within the participant clinical file, along with any instructions or changes regarding the infusion.

8.10 Exit assessments

Participants will be visited in the morning following the last dose of the study intervention prior to discharge (last day of data collection, or when treatment is ceased, if earlier cessation occurs) for collection of exit data. During the visit, the study nurse will take the measures and assessments as outlined in 8.1 Table of study measures and record the visit in the CRF. This visit will also be recorded within the participant clinical file, along with any instructions or changes regarding ongoing management.

8.11 Withdrawal assessments

If participants are to be withdrawn, a 'Withdrawal Case Report Form' will be completed by the study nurse on instruction from the investigator. The assessments and reason for withdrawal will be recorded. Withdrawal will be initiated if the participant meets any of the withdrawal criteria as described in section 5.13 Cessation of study medicine. All associated

documents will be completed (Serious Adverse Event report, adverse event assessment score etc).

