5.12 Cessation of study drug

- Participant request
- Unacceptable side effects from study medications (defined by National Cancer Institute Common Criteria for Adverse Events; CTCAE version 4.0).
- Participants who in the opinion of the investigator are not well enough to continue the study (Specific reasons for withdrawal need to be documented in the Case Report Form)
- Treatment deemed ineffective by treating clinician, who wishes to use alternative therapy.
- Occurrence of delirium (completion of study)
- Can no longer swallow
- Discharge from Hospital (completion of study)
- The participant withdraws their consent, with or without consent to use already collected data.
- It is inappropriate to continue the study medication for whatever reason

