5.13 Post study treatments

All participants will be followed by their clinician for continuing care, irrespective of the point at which they exit the study.

Treatment continuation: Melatonin will only be available for currently approved indications (primary insomnia) if the participants meets that indication, after study completion (on discharge). The treatment available to reduce delirium risk after discharge will be determined by the treating clinician, and can include individualised strategies to reduce risk of delirium including regular exercise as tolerated, maintaining vision and hearing or using aids, regular reorientation and non-medication methods to improve sleep (quiet room, relaxation for example).

In all study participants, regardless of above choices, secondary outcomes and collection of data for will occur until the end of the inpatient admission after randomization, unless consent is withdrawn

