6.0 OUTCOMES AND MEASURES

6.1 Primary outcome and measure

Delirium-free days (which occur before delirium onset for any participant who develops delirium).

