7.9 Safety assessment

Safety assessments are made at all participant contacts as described earlier. All safety assessments are made before efficacy assessments. If burden, side effects or safety issues are identified, continuation in the study will be stopped.

In the event of an adverse event clinicians will manage the event according to best medical practice.

Further, the research nurse who visits the participants and their carers will also ask about any other unexpected adverse outcomes. The study investigators will oversee this research nurse. All serious adverse events will be reported to the Research and Ethics Committee within 24 hours (see section 9.0 Adverse Events). Other adverse events will be described in the Annual Report to the Committee.

Serious adverse events will be followed until documentation of resolution or the successful initiation of relevant management strategies.

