8.12 Follow-up phase assessments

Participants will enter a follow-up phase irrespective of their place of care until death or 21 days after ceasing the study medication (whichever is the shorter period); or if withdrawal of consent occurs. During the follow-up phase frequency of adverse events, delirium (based on medical record), quality of life, performance status, medication and health service usage will be collected.

Follow-up data will be collected by the study nurse weekly by telephone for up to 21 days. A medication list will be updated at each contact to record actual prescribed and taken medications since the preceding visit.

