11.2 Statistical analysis of efficacy primary outcome

Intention-to-treat analysis will be used for all statistical comparisons. For the primary outcome, comparisons between groups for delirium-free days, with adjustment to the length of stay and other potential covariates using a general linear model approach will be undertaken. For potential missing data, multiple imputation technique will be applied to handle the missing data. A proper multiple imputation method will be employed that based on various models of assumption including missing completely at random (MCAR), missing at random (MAR), and missing not at random (MNAR). Sensitivity analysis will apply to examine the effects of these different assumptions on the imputed data structure in order to ascertain the most reliable approach.

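### The protocol contradicts itself on whether delirium ratings continue in an inpatient who has stopped study drug, which leaves ascertainment of the primary endpoint open to informative loss

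*Protocol*

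**What the plan says.** The primary outcome (6.1) is "Delirium-free days (which occur before delirium onset for any participant who develops delirium". Section 11.2 states: "Intention-to-treat analysis will be used for all statistical comparisons".

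One group of sections ties the end of assessment to the end of study drug:

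- 8.11: "Withdrawal will be initiated if the participant meets any of the withdrawal criteria as described in section 5.13 Cessation of study medicine". Section 5.13 is in fact headed post study treatments; the cessation list is 5.12.
- 5.12 mixes withdrawal of consent with reasons that concern only the drug, among them side effects, being too unwell in the investigator's opinion, and "Can no longer swallow".
- 7.9: "If burden, side effects or safety issues are identified, continuation in the study will be stopped".
- 8.10 schedules the exit visit for the "last day of data collection, or when treatment is ceased, if earlier cessation occurs) for collection of exit data".
- 8.12 starts follow-up at drug cessation, wherever the participant is being cared for. Contact is by weekly telephone call, and the data include "frequency of adverse events, delirium (based on medical record), quality of life, performance status". The footnote to table 8.1 uses the same starting point. The table places no DRS-R-98, NuDESC or RASS in the Discharge or Follow-up columns.

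A second group implies that assessment runs to the end of the admission:

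- 5.13: "regardless of above choices, secondary outcomes and collection of data for will occur until the end of the inpatient admission after randomization". The one exception given there is a participant who takes back consent.
- 5.14 limits the weekly calls to participants who have gone home.
- 7.2 sets the study period to discharge or death.
- 7.7.1 repeats DRS-R-98 every three days for the remainder of the admission, plus on defined triggers. 7.7.2 has ward nurses complete NuDESC on each of three shifts.
- 8.9 has the study nurse visit daily on the inpatient unit, with no condition on taking tablets.
- 13.1.1 lists separate case report forms for treatment cessation and for withdrawal.

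**The concern.** Delirium-free days can be counted only if the day of onset is observed. Several reasons for stopping the drug are signs of decline, and section 1.1 cites delirium in up to 90% of patients in the days and hours before death. If ratings stop when tablets stop, observation ends for prognostic reasons at a time when delirium is likely. Missingness of the primary endpoint would then depend on the outcome itself.

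Sites could also differ. One working from 8.10 to 8.12 would use the chart after cessation, while one working from 5.13 and 7.7.1 would go on rating at the bedside. The protocol itself treats bedside capture as important: 7.7.2 screens every shift so that incident delirium is not missed, and section 1.3 reports that the pilot showed the need for qualified research staff to capture weekend events.

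**Working it through.** No figure in the plan depends on this rule, so the check is to follow one participant through both groups of sections. Take someone still in hospital and not delirious who can no longer swallow tablets.

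**Under 8.10 to 8.12.** The 5.12 criterion is met, so 8.11 starts withdrawal. Exit data are taken the next morning (8.10). The participant enters the telephone phase although still on the ward (8.12). Table 8.1 schedules no delirium instrument in that phase.

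**Under 5.13, 5.14, 7.2, 7.7.1, 7.7.2 and 8.9.** Data collection continues to the end of the admission. The telephone phase does not apply, because the participant has not gone home. Ratings stay on schedule.

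**Scheduled ratings per inpatient week after day 7:**

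| | Second group | 8.10 to 8.12 |
|---|---|---|
| NuDESC | 3 shifts x 7 days = 21 | 0 |
| DRS-R-98 | 7 / 3, so 2 or 3, plus triggers | 0 |
| RASS-Pal | 7 | 0 |
| Telephone contact | none needed | 1, with delirium from the record |

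In the first 7 days DRS-R-98 is daily, so the contrast is one DRS-R-98 a day against none.

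**Does any sentence settle it?** 5.13 comes closest, but it names only secondary outcomes, has a word missing, and sits under a heading about treatment after the study. 7.2 defines a period and lists no assessments. 7.7.1, 7.7.2 and 8.9 do not mention participants who have stopped drug or been withdrawn. The two CRFs in 13.1.1 show that a distinction was intended, but 8.11 removes it. Nothing clearly decides the matter for the primary endpoint.

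**After delirium onset.** 5.12 labels delirium as completion of study, yet 7.7.1 assesses severity, duration and resolution after onset. By the definition in 6.1 this cannot affect the primary outcome. It touches secondary outcomes only.

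**Illustration of direction only; every input is an assumption.** Take 21-day delirium risks p of 40% (placebo) and 25% (melatonin), constant hazard λ = −ln(1 − p)/21, and mean delirium-free days p/λ.

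- Placebo: λ = 0.0243, mean 16.44 days. Melatonin: λ = 0.0137, mean 18.25 days. The difference is about 1.8 days.
- In a simulation, 10% to 30% of each arm stops drug at a uniformly distributed time between days 1 and 21, and the delirium hazard after stopping is 1 to 5 times the earlier one. With full ascertainment the difference is 1.8 to 2.0 days.
- If delirium after stopping is never recorded and the participant counts as delirium-free to day 21, it is 1.7 to 1.8 days.
- If counting is cut at drug stop, it is 1.5 to 1.7 days.

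With equal stopping in both arms the difference shrinks, against a design target of 2 days (11.5). Unequal stopping was not modelled.

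**The case against.** The best defence is that the protocol, read as a whole, intends inpatient assessment to continue. 5.14 confines telephone contact to people at home, 7.7.1 and 7.7.2 are not conditional on study drug, and a separate Treatment Cessation CRF exists. Read literally, 8.11 would also make delirium and discharge withdrawals, although 5.12 marks both as completion of study; that suggests loose drafting. Participants also stay in follow-up after cessation, with delirium taken from the record, and 11.2 plans multiple imputation with a missing-not-at-random sensitivity analysis.

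Much of this stands. A reader might infer from 8.10 to 8.12 alone that the protocol has a settled rule and that inpatients certainly lose their ratings on stopping drug. The documents do not support that, because the contrary sections are equally current. Nor is it correct that severity and duration after onset would go unobserved, since 7.7.1 says they will be assessed.

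The defence does not remove the contradiction. Record-based capture and imputation mitigate missing ratings, but they do not replace onset dates that could have been obtained at the bedside.

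**Conclusion.** The point holds as an unresolved contradiction that bears on the primary endpoint. Sites following 8.10 to 8.12 can lose the scheduled ratings for reasons linked to impending delirium, which would make missingness informative and weaken the intention-to-treat comparison.

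The number of events at risk cannot be derived from the documents. A reader might take the 30% allowance in 11.5 (0.30 x 220 = 66) and apply the 20% to 45% inpatient incidence from 1.1 to obtain 13 to 30 affected events. That is not supported. The allowance covers drop-out and loss to follow-up, and is not a forecast of inpatients who stop drug. A whole-admission incidence also ignores the time already observed before stopping, and the documents give no rate at which charts miss delirium. The simulated differences above show direction under stated assumptions and are not estimates for this trial. Greater stopping in one arm would be a further source of bias, but nothing in the protocol shows that it is expected; section 1.3 reports that the pilot intervention was well tolerated.

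**What to change.** Reconcile 5.12, 5.13, 5.14, 7.2, 7.9, 8.1 and 8.10 to 8.12, and correct the cross-reference in 8.11 to 5.12. The revised text should state that:

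1. stopping study drug is not withdrawal from the study, and the Withdrawal CRF is used only when consent to further data is withdrawn;
2. unless consent is withdrawn, NuDESC, DRS-R-98 and RASS-Pal continue on the existing schedule for every randomised inpatient until delirium, discharge, death or the end of the 3-week period, whatever the drug status;
3. ratings after delirium onset continue as 7.7.1 already describes, with the completion label in 5.12 reworded to match;
4. the telephone, record-based phase starts at discharge;
5. the 5.13 commitment names the primary outcome, and its missing word is supplied.

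These changes concern data collection only and leave the reasons for stopping drug as they are. The cost is protocol and CRF wording, plus continued ratings by ward and study nurses for participants who are off drug but still in hospital. The change has to be made before the data are collected, because ratings not taken at the bedside cannot be recovered afterwards.

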8.12 Follow-up phase assessments

Participants will enter a follow-up phase irrespective of their place of care until death or 21 days after ceasing the study medication (whichever is the shorter period); or if withdrawal of consent occurs. During the follow-up phase frequency of adverse events, delirium (based on medical record), quality of life, performance status, medication and health service usage will be collected.

Follow-up data will be collected by the study nurse weekly by telephone for up to 21 days. A medication list will be updated at each contact to record actual prescribed and taken medications since the preceding visit.

8.13 Economic evaluation

The data collected in the follow-up phase (8.12) will inform the economic evaluation, and includes longer term clinical and economic outcomes.

9.0 ADVERSE EVENTS

9.1 Reporting of adverse events

All adverse events will be reported via an online reporting system to enable study wide reporting. The Palliative Care Clinical Studies Collaborative (PaCCSC) has a Standard Operating Procedure for Adverse Event reporting (5.17, Adverse Event Reporting) that will operate at all study sites. In addition there will be specific events and reporting mechanisms required due to the nature of the study medicine. This is described below.

9.2 Criteria for assessing severity

Severity of adverse events will be assessed according to Good Clinical Practice guidelines ⁶⁹ and National Institutes of Health Common Terminology Criteria for Adverse Events⁷⁰.

9.2.1 Adverse events

Adverse events are defined as any untoward or unexpected occurrence in a patient or clinical investigation participant where the occurrence does not necessarily have a causal relationship with the study intervention.

There are circumstances where adverse events will not be reported. Examples are;

- An expected side effect from a study intervention, such as constipation unless the side effect required additional treatment or assessment
- Signs or symptoms associated with the disease or disorder under study, unless they are more severe than expected.
- Social admission to hospital

9.2.2 Serious adverse events

Serious Adverse Events are any untoward medical occurrence that meets one or more of the following criteria/outcomes;

- death
- life-threatening (i.e. at immediate risk of death)
- in-patient hospitalisation or prolongation of existing hospitalisation
- persistent or significant disability/incapacity
- congenital anomaly or birth defect
- other medically relevant condition judged as serious

The expected study population have an underlying disease that is expected to significantly shorten life expectancy, they are already termed palliative and are expected to die within a short period of time.

The conditions recognised as being excluded from SAE reporting are as follows:

- Where participants are admitted as a planned admission due to respite, family or social issues, or for pre-planned treatment
- Where participants are admitted (or admission is prolonged) due to a documented expected deterioration in their condition due to the underlying disease process, or where the admission is prolonged for this reason
- Where participants die due to a well documented decline in their condition due to the underlying disease process

"Life threatening" means that the participant was at immediate risk of death from the event as it occurred. It does not include an event that, had it occurred in a more serious form, might have caused death.

"Requires inpatient hospitalisation" is defined as hospital admission for treatment of the adverse event. Hospital admission for scheduled elective surgery would not be a serious adverse event.

"Other medically relevant condition judged as serious" is where medical and scientific judgment should be exercised in deciding whether expedited reporting is appropriate in other situations, such as important medical events that may not be immediately lifethreatening or result in death or hospitalisation but may jeopardise the participant or may require intervention to prevent one of the other outcomes listed in the definition above. These should also usually be considered serious. Examples of such events are intensive treatment in an emergency room or at home for allergic bronchospasm; blood dyscrasias or convulsions that do not result in hospitalisation; or development of drug dependency or drug abuse. A diagnosis of a new cancer during the course of the treatment should be considered as medically important.

Progression of a participant's underlying condition leading to one of the above should always be reported as a serious (but expected) adverse event, which is unrelated to protocol treatment, or caused by failure of the anticipated therapeutic effect of the study drugs.

In all other cases, serious adverse events will be reported according to the requirements of the local Hospital Ethics Committee.

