5.14 Follow-up

During the follow-up phase frequency of adverse events, delirium (based on medical record), quality of life, medication and health service usage will be measured up to death or 21 days after ceasing study medication (whichever is the shorter period). These data will be collected via a weekly telephone call to the participant if they have been discharged home. Carer experience will also be captured using the Carer Experience Scale.

We will record the date of death for all participants where possible, including post recruitment. The census date will be 28 days after recruitment of the last participant to the study.

Economic evaluation

Limited evidence suggests that interventions to prevent delirium or reduce its duration in hospital are cost effective, ^{57,58} with the majority of cost offsets from longer term care savings. ⁵⁷ Estimating cost offsets over shorter time frames is crucial given advanced cancer has limited prognosis, and in prior cost-effectiveness studies, patients with terminal illness were excluded. ³⁴ The cost-effectiveness sub-study will evaluate the within-study incremental resource use, cost and consequences of melatonin relative to placebo for preventing delirium in advanced cancer patients from randomisation to study end or death (whichever is sooner). The analysis will include efficacy (delirium-free days), toxicity, survival and resource data (intervention costs, hospital length of stay, health professional time, medication use and investigations). Sampling and parameter uncertainty will be estimated by bootstrapping on participants' costs and effect pairs to maintain covariance in re-sampling with replacement across 10,000 replicates. Cost-effectiveness acceptability curves, sensitivity and scenario analyses will be undertaken.

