8.0 STUDY PROCEDURES

8.1 Table of study measures

	Eligibility	Baseline	Daily	Delirium occurrence	Discharge	Follow-up [#]
Investigations				occurrence		
Liver function	*			*		
Electrolytes	*			*		
Full blood count	*			*		
Measures						
Medical file review						
Demographics	*					
Diagnosis	*					
Con meds	*	*	*	*	*	*
Prn medications		*	*			
Specific medications:		*	*	*		*
Anticholinergics,						
corticosteroid and						
benzodiazepines						
CYP1A2 inhibitors						
(quinolones,						
carbamazepine,						
rifampicin,						
fluvoxamine)						
Warfarin						
Vital signs		*	*	*		
Admission data		*				
Preventative care		*	*	*		
non-						
pharmacological						
measures						
Survival					*	*
Falls			*		*	*
Pressure areas			*		*	*
Pneumonia			*		*	*
Length of stay					*	
Health services		†			*	*
utilisation						
In hospital		†	*		*	
resource utilisation						
Patient measures						
Vision	*					
Hearing	*					

	Eligibility	Baseline	Daily	Delirium occurrence	Discharge	Follow-up [#]
AKPS	*	*		*	*	*
Short Blessed Test		*			*	
Insomnia Severity Index		*	Every five days			
Quality of life (EQ- 5D-5L)		*			*	*
Medical assessment	*		*			
Delirium Experience Questionnaire					* (only if delirium occurred)	* (only if delirium occurred)
Clinician assessed						
Toxicity		*	*	*		*
Charlson Comorbidity Index		*				
Sedation (RASS)		*	*			
DRS- R-98	*		Daily for 7 days.	*		
NuDESC	*	*	* each shift			
Delirium Etiology Checklist		*		*		
Carer measure						
Delirium Experience Questions				*		* (only if delirium occurred in participant)
Carer Experience Scale		*		*		*

[#] Measured up to death or 21 days after ceasing study medication (whichever is the shorter period) by weekly phone call.

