9.3.1 Time period for assessing AE's and SAE's

At each visit, the participants are encouraged to mention any problems since the last visit. In addition, the following standard questions should be asked;

- 1. Have you had any medical problems since the last visit or study assessment?
- 2. Have you started any new medications, other than given to you in this study, since the last visit or assessment?

For all randomised participants all AE's, irrespective of causality, will be assessed and recorded as per the standard operating procedures. The time period includes the time from randomisation, the inpatient treatment period and the 4 week extension phase (by telephone).

For patients who meet the eligibility criteria and then do not proceed to randomisation, any AE's detected during that window of time, should be reported. If an AE is the reason that a person does not proceed to randomisation, this should be recorded within the CRF, adverse event report and in the clinical record, irrespective of causality or seriousness.

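### Section 9.2.2 gives opposite rules for reporting disease progression as an SAE, the 9.3.1 adverse-event period outlasts the scheduled contacts by a week, and follow-up is timed from drug cessation

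*Protocol*

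**What the plan says.** **SAE rule.** Section 9.2.2 lists conditions that are excluded from SAE reporting. One is "Where participants die due to a well documented decline in their condition due to the underlying disease process"; another covers admissions, or prolonged admissions, for documented expected deterioration from the disease. The same section later says that progression of the participant's "underlying condition leading to one of the above should always be reported as a serious (but expected) adverse event".

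**AE rule.** Section 9.2.1 gives examples of adverse events that will not be reported, among them "An expected side effect from a study intervention, such as constipation unless the side effect required additional treatment or assessment". Section 9.3.1 says that, for all randomised participants, all adverse events, "irrespective of causality, will be assessed and recorded as per the standard operating procedures".

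**Period.** Section 9.3.1 defines the AE/SAE period as the time from randomisation, "the inpatient treatment period and the 4 week extension phase (by telephone"). Section 8.12 says "Follow-up data will be collected by the study nurse weekly by telephone for up to 21 days". The footnote to the table in section 8.1 says "Measured up to death or 21 days after ceasing study medication (whichever is the shorter period) by weekly phone call", and section 5.14 agrees with it.

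**When the drug stops.** Sections 5.1 and 5.12 end study medication at delirium, at discharge, after a maximum of three weeks, or for other reasons such as side effects, inability to swallow or participant request.

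**The concern.** Adverse effects and in-hospital complications are secondary objectives (section 2.2.2). Sections 9.7 and 11.6 have adverse events compared between groups at two interim looks, with p<0.001 as the stopping threshold. What counts as a reportable serious event should therefore be settled before the first look and be the same at every site. Section 9.2.2 itself expects participants to die within a short time, so the event on which its two rules disagree is likely to be the most frequent serious event in the trial.

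The period matters for a similar reason. Section 9.5.1 uses the section 9.3 period to separate in-study from post-study events, and investigators need not actively seek the latter. If the period runs longer than the contacts, the last week belongs to the study on paper, but nobody is scheduled to ask about it.

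The start of the clock is a separate weakness. If follow-up begins at an event that the treatment is meant to influence, participants are observed for different lengths of time for a reason tied to the primary outcome. Raw event counts are then not strictly comparable.

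**Working it through.** The protocol states no total observation time and no expected difference between arms, so there is no figure of its own to reproduce. The check compares texts and does window arithmetic.

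**1. The two SAE rules side by side.** Take a participant who dies after a documented decline from cancer.
- The exclusion list in 9.2.2 says the death is not reported as an SAE.
- The later paragraph of 9.2.2 says progression that meets an SAE criterion is always reported; death is the first criterion listed.

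The same conflict arises for admission or prolonged stay. The two rules give opposite instructions for one event.

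**2. AE period against contacts.**
- Period under 9.3.1: 4 weeks = 28 days of telephone phase.
- Contacts under 5.14, 8.1 and 8.12: up to 21 days after cessation.
- Gap: 28 − 21 = 7 days (days 22 to 28), or 7/28 = 25% of the telephone phase. This takes the 4-week phase to start when the drug stops; 9.3.1 does not say so in terms.

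**3. Scheduled observation from randomisation.** Formula: cessation day + 21.
- Cessation on day 1: 1 + 21 = 22.
- Cessation on day 2: 2 + 21 = 23.
- Cessation on day 21 (the maximum): 21 + 21 = 42.
- Ratio of longest to shortest: 42/22 = 1.91.
- With 28 days in place of 21, the range is 29 to 49.

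**4. Possible difference between arms.** Assumption: mean cessation day equals the pilot's mean delirium-free days in section 1.2/1.3 (20.0 melatonin, 17.9 control). This ignores discharge, death and other reasons for stopping.
- Melatonin: 20.0 + 21 = 41.0 days.
- Placebo: 17.9 + 21 = 38.9 days.
- Difference: 2.1 days; 41.0/38.9 = 1.054, about 5% more observation.
- With the 28-day text: 48.0 against 45.9, about 4.6%.
- If melatonin changes neither delirium nor discharge timing, the expected difference is zero and only the inequality between participants remains.

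**5. Is a common window available?** The earliest end of scheduled follow-up is day 22. A window from randomisation to Day 21 therefore lies inside the schedule for every participant who has taken a dose, is alive and has not withdrawn consent.

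**The case against.** **Recording is not reporting.** A reader might infer that expected drug effects and most deaths drop out of the data. The documents do not support this. Section 9.3.1 requires all adverse events to be recorded, section 5.14 records the date of death for all participants where possible, and section 5.13 continues secondary data collection to the end of the admission. Falls, pressure areas, pneumonia, survival and toxicity are scheduled measures in section 8.1, and section 9.3.2 grades named symptoms at each visit. Sections 9.2.1 and 9.3.1 can be read together as a reporting rule and a recording rule. This objection stands. What remains is that the protocol never states the distinction.

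**The 9.2.2 rules might be reconciled.** One could confine the exclusion to documented, expected decline and apply the later paragraph to other progression. That does not work, because the later paragraph says always and itself classes these events as expected.

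**Unequal windows need not bias the comparison.** The objective concerns in-hospital complications, and nothing says they will be compared over the whole period after cessation. Participants who stay in hospital are also observed to the end of the admission, so 22 to 42 days describes the scheduled follow-up and not always the full observation. A reader might infer that melatonin will collect more events because its arm is watched longer. The 2-day figure is only a proxy, and shorter hospital stay is itself a hoped-for benefit, which would shorten the melatonin window. This stands: the direction is not known. An SAP could also fix the comparison window. It could not repair a site reporting rule or contacts that were never scheduled.

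**Costs.** The Trial Summary and section 7.10 already give 21-day horizons. Sections 5.14 and 11.4 run to study end or death. Unequal cost windows would follow only if the analysis used all data to the end of follow-up, so the point reduces to stating one origin and one length.

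**Census.** Because 21 + 21 = 42 exceeds 28, a reader might infer that late recruits lose up to 14 days of follow-up. The sentence "The census date will be 28 days after recruitment of the last participant to the study" comes directly after the one on recording dates of death and most naturally governs survival. Nothing says that telephone follow-up or AE collection stops there.

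**Conclusion.** Two contradictions are established from the text alone. Section 9.2.2 both excludes and requires SAE reports for disease progression, and 9.3.1 sets an AE period one week longer than the contacts in 5.14, 8.1 and 8.12. The first makes the SAE counts seen by the monitoring committee depend on site practice. The second leaves a quarter of the telephone phase without active enquiry.

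That follow-up starts at an outcome-dependent time is also established, with a range of up to 1.9-fold between participants. Its effect on the comparison of arms is not established: about 5% under the pilot proxy, zero if melatonin has no effect on timing, and possibly in the other direction if melatonin shortens stay. The review does not claim that safety data are missing or that the census truncates follow-up.

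These points should be corrected before the first interim look. They do not call the design into question.

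**What to change.** - **Section 9.2.2:** reconcile the exclusion list with the later paragraph so that one SAE rule for disease progression applies at all sites. Which rule to keep is for the sponsor to decide.
- **Sections 9.2.1 and 9.2.2:** state that the exclusions limit what is reported and leave the recording required by 9.3.1 untouched.
- **Section 9.3.1:** align the AE/SAE period with the scheduled follow-up in 5.14, 8.1 and 8.12, so that 9.5.1 also refers to a period that is actually covered.
- **Comparison between arms:** compare adverse events and complications over a common window from randomisation to Day 21, and use the same 21-day horizon from randomisation for costs. Later data can still be described.
- **Section 5.14:** say that the 28-day census applies to survival, if that is what is meant.

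The cost is a wording amendment and a note to sites. No extra visits or contacts are needed, and the data for the common window are already scheduled.
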